### 3.5 Secondary Endpoints

- Safety evaluation, as measured by rate and severity of adverse events (AE), serious adverse events (SAE), and serious unexpected serious adverse reactions (SUSAR).
- Size of the functional, latent HIV-1 reservoir as determined by the number of infectious units per  $10^6$  resting memory CD4+ T cells (IUPM) using a viral outgrowth assay before and after therapy. Post therapy measurements will occur after the second cycle, just before ATI. These measurements will be performed in [name] laboratory.
- Size of the proviral HIV-1 reservoir as determined by total HIV-1 DNA and episomal HIV-1 DNA (2-LTR) in circulating total CD4+ T cells at baseline, after each romidepsin cycle, prior to the ATI period (week 24), and at the end of the study (week 48).
- Plasma HIV-1 RNA, as measured by a routine clinical assay (Cobas Taqman; detection limit 20 copies/mL), a transcription mediated amplification (TMA)-based assay (detection limit 12 copies/ml) and/or a single copy assay (detection limit 1-2 copies/mL).

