### **6.2.12 Antiretroviral and Immunogenicity Assessments**

HIV-1 levels will be assessed by (Appendix A):

1. Standard HIV-1 viral load assay (Cobas Taqman) (CLEP-certified) will be performed at a contracted laboratory, LabCorp (RUH site) and at the AUH and CUH clinical virology labs. The detection range of the assay is 20-10x10^6 copies/ml. HIV-1 viral load will be determined at multiple time points before and after 3BNC117 administration.
2. Transcription mediated amplification is a qualitative method to detect plasma HIV-1 RNA (Procleix Ultrio Plus, Genprobe). It has 50% sensitivity at 3.8 copies/mL and 95% sensitivity at 12 copies/mL. TMA results are considered binary and defined as positive or negative according to assay outcomes.
3. Single copy assay has a detection limit of 1-2 copies HIV-1 RNA/mL of plasma. This assay will be performed in the Laboratory of Molecular Immunology. This

assay will be performed on samples collected at baseline (week -2 and day 0), and 1 day after the second romidepsin infusion in each treatment cycle.

4. HIV-1 cell-associated unspliced HIV-1 RNA dd PCR assay. This assay provides an accurate quantification of HIV-1 transcriptional activity and will be performed at the AUH site. This assay has a limit of detection of 1 HIV-RNA copy per 1 million CD4+ T cells.
5. HIV-1 cell associated DNA levels in CD4+ T cells will be measured at the AUH site, before and after administration of 3BNC117. This assay has a limit of detection of 10 DNA copies per 10^6 CD4+ T cells. This assay will be performed at the AUH site.
6. The size of the functional HIV-1 reservoir will be determined by the number of infectious unit per 10^6 resting memory CD4+ T cells (IUPM) using a viral outgrowth assay before (week -2) and after therapy, just before ATI (week 22).

Given the large number of cells required for this assay, viral outgrowth assays will not be performed at a later time point. The size of the reservoir in participants who remain virologically suppressed during ATI or are re-suppressed following ART resumption will be evaluated by levels of cell-associated HIV-1 DNA, performed at week 48.

In addition, the effects of 3BNC117 on host immune responses and on circulating HIV-1 strains will be evaluated by the following assays (Appendix A):

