### 2. Size of the functional HIV-1 reservoir:

The size of the functional HIV-1 reservoir will be determined by the number of infectious unit per  $10^6$  resting memory CD4+ T cells (IUPM) using a viral outgrowth assay before (week -2) and after therapy, just before ATI (week 22). Paired student t-test or paired Wilcoxon test will be used to determine changes in reservoir size from baseline to the pre-ATI time-point for each group.

Total HIV-1 DNA, episomal HIV-1 DNA (2-LTR), and unspliced HIV-1 RNA in circulating total CD4+ T cells will also be determined at baseline (week -2, week 0), before and after each treatment cycle, at the pre-ATI time point (week 24), and at the end of the study (week 48). A 95% repeated measures ANOVA F-test will be used to compare changes in these variables during the study.

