### **8.2 Sample Size Considerations**

The sample size calculation is based on the primary analysis for the primary endpoint. We will compare days from day of ART interruption until day of viral rebound or day of reinitiation of ART without viral rebound in arm A to arm B (1:1 randomization) with the Wilcoxon-Mann-Whitney test. Given a standard deviation (SD) of 10 (days), enrolling 12 patients in each of the two arms, will have 80% power to detect  $\geq 13$  days difference in time to viral rebound at a 5% significance level ([Davey et al., 1999](#); [Hamlyn et al., 2012](#); [Hill et al., 2014](#)). The power calculation for this primary analysis was performed in G\*power using the minimum Asymptotic Relative Efficiency method.

To accommodate for dropouts, we aim to enroll 30 study subjects in the study (15 in each arm). A dropout rate of ~20% is anticipated.

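### The repeated measures ANOVA for the HIV-1 DNA and RNA markers has no missing-sample rule, sphericity correction or named contrast; a mixed model on all available samples would serve better

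*Combined protocol and SAP*

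**What the plan says.** Section 8.1 (Secondary and Exploratory Endpoints, item 2) covers total HIV-1 DNA, episomal 2-LTR DNA and unspliced HIV-1 RNA in CD4+ T cells with one sentence: "A 95% repeated measures ANOVA F-test will be used to compare changes in these variables during the study". The viral outgrowth measure (IUPM) in the same item has its own paired test and is not part of this point.

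The sampling times differ between sections. Section 8.1 lists two baselines (weeks -2 and 0) and then "before and after each treatment cycle, at the pre-ATI time point (week 24), and at the end of the study (week 48"), which makes seven occasions when week 0 serves as the sample before cycle 1. Section 3.5 lists "at baseline, after each romidepsin cycle, prior to the ATI period (week 24), and at the end of the study (week 48"), which makes five. Section 3.5 makes the two DNA measures secondary endpoints; section 3.6 makes unspliced RNA exploratory.

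On missing data, section 8.2 says "A dropout rate of ~20% is anticipated", while the Statistical Methodology part of the Study Schema expects 5-15%. Section 6.1.10.6 does not replace participants withdrawn after a dose but follows them to their final planned visit where possible. Section 6.2.12 describes the week-48 assessment this way: reservoir size "in participants who remain virologically suppressed during ATI or are re-suppressed following ART resumption will be evaluated by levels of cell-associated HIV-1 DNA". For the DNA assay the same section states "This assay has a limit of detection of 10 DNA copies per" million CD4+ T cells; for unspliced RNA the limit is one copy per million. Section 8.1 (item 5) allows a log2 transformation if needed.

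No section states the effect tested (time or arm-by-time), a sphericity correction, a covariance structure, a missing-sample rule, or how values below the limit enter the test.

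**The concern.** Two features of the named method fit this sampling plan poorly.

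First, a classical repeated measures ANOVA needs a complete row per participant. One missed sample removes all of that person's data, including samples taken during treatment. In a trial of 30 with expected dropout and samples spread over about a year, that can be costly. If week 48 is missing because a participant is still viremic, the remaining complete rows are also a selected group.

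Second, the within-person F-test holds its level only if the differences between every pair of visits have equal variance (sphericity). With gaps from about 2 to 24 weeks, close visits may be more alike than distant ones. Week 48 may also be more variable, because it follows the treatment interruption, with some participants possibly still off ART and others re-treated (section 6.1.7). Either pattern pushes an uncorrected test above 5%.

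At stake is the reading of the reservoir objective in section 3.3. The trial is open-label (section 6.2.2), so leaving the contrast, the correction and the missing-data rule open also allows them to be chosen after the data are seen.

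**Working it through.** **Figures in the plan.** The documents give no power or error figure for this test beyond the 95% label, read here as a 5% level. The enrolment arithmetic in section 8.2 reproduces: 24 / (1 - 0.20) = 30.

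**Step 1: complete rows.** Inputs: 30 enrolled (section 8.2); dropout d of 5% (lowest Study Schema figure) to 20% (section 8.2); k = 5 visits (section 3.5) or 7 visits (section 8.1). The share m of samples missed per visit is not given; 2%, 5% and 10% are assumed, independent across visits. Every dropout is taken to lack at least one sample.

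Expected complete participants = 30 x (1 - d) x (1 - m)^k. For example, at d = 20%, m = 5%, k = 7: 24 x 0.95^7 = 24 x 0.698 = 16.8.

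| Missed per visit | 20% dropout, 7 visits | 20% dropout, 5 visits | 5% dropout, 7 visits | 5% dropout, 5 visits |
|---|---|---|---|---|
| 2% | 20.8 | 21.7 | 24.7 | 25.8 |
| 5% | 16.8 | 18.6 | 19.9 | 22.1 |
| 10% | 11.5 | 14.2 | 13.6 | 16.8 |

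Dropout alone, with no other missed sample, leaves 24 to 28.5 of 30.

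**Step 2: type I error if no correction is applied.** The documents give no correlation or variance by visit for these markers, so the covariance is assumed over a range. Simulation: two groups of 15, no true change, 40,000 trials per scenario, time and arm-by-time F-tests at a nominal 5%. Assumed visit weeks were -2, 0, 4, 8, 12, 24, 48 (seven visits); 0, 4, 8, 12, 24, 48 (six); and 0, 3, 11, 24, 48 (five). The weeks for the samples after each cycle are assumptions.

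| Assumed covariance | Uncorrected type I error |
|---|---|
| Equal variances and correlations (compound symmetry) | 4.9-5.2% |
| Stable person effect + decay + independent assay noise | 5.1-6.4% |
| Pure decay, 4-week correlation 0.5 to 0.95, seven visits | 6.7-10.3% |
| Same, six visits | 5.9-9.5% |
| Same, five visits | 5.7-9.0% |
| Equal correlations, week-48 SD x 1.5 | 6.2-6.6% |
| Equal correlations, week-48 SD x 2 | 8.6-9.6% |

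A separate run with 24 participants gave 6.8-9.9% (seven visits) and 5.1-7.7% (five visits) under decay without noise, and about 5.0-5.7% once assay noise was added. A stable person effect by itself changes nothing, because it cancels from within-person differences. What matters is how decay compares with noise, and whether the variance changes by visit.

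**Step 3: with a correction.** Over all scenarios, the Greenhouse-Geisser correction gave 3.4-5.1%. The Huynh-Feldt correction, run for the time test only, gave 4.7-5.9%. Both still need complete rows, so they repair Step 2 but not Step 1. The mixed model was not simulated.

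**The case against.** The strongest reply is that the plan is brief rather than wrong. It says neither that the F-test will be uncorrected nor that incomplete participants will be dropped. A Greenhouse-Geisser correction or a mixed-model version is not excluded. That stands, and it limits the point to what the standard form of the named test does and what the plan leaves open.

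A reader might infer that the unequal visit gaps make the test run at 7-10%. The documents do not support this. Under compound symmetry the level is about 5% whatever the spacing, and with realistic assay noise it may stay near 5-6%. The upper range needs strongly decaying correlation or a much larger week-48 variance, and neither is given.

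A reader might also infer that a third or more of the trial would be lost. That depends on assumed rates. At 20% dropout, seven visits and 2% missed samples the loss is (30 - 20.8) / 30 = 31%; at 5% dropout and five visits it is (30 - 25.8) / 30 = 14%. Follow-up of withdrawn participants where possible (section 6.1.10.6) and the 10% over-enrolment that section 10 allows for dropouts would both reduce the loss.

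Finally, one of the three markers is exploratory, and none is the primary endpoint. These replies reduce the size of the point. They do not supply the missing contrast or missing-data rule, and they do not remove the need for complete rows.

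**Conclusion.** The concern holds as a weakness in method and specification for two secondary endpoints and one exploratory endpoint. In its standard form, the named test would use about 21-26, 17-22 or 11.5-17 of 30 participants at 2%, 5% or 10% missed samples per visit. These counts rest on the stated 5-20% dropout, five to seven visits, independent missed samples and no complete rows from dropouts. Loss at week 48 may be related to outcome, given how section 6.2.12 describes who is evaluated then.

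Without a sphericity correction, type I error lies somewhere between 5% and about 10%. The documents do not allow a narrower statement, so excess false findings are possible but not shown. The loss of incomplete participants is the firmer of the two reasons to change the method. The primary comparison of time to rebound is not affected.

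**What to change.** Replace the sentence in section 8.1 with the following elements:

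- **Model:** a linear mixed model for each marker on log-transformed values, using all available samples, with fixed effects for arm, visit and arm-by-visit, and the mean of weeks -2 and 0 as baseline covariate.
- **Covariance:** a random intercept plus spatial-power correlation in time, with Kenward-Roger degrees of freedom. An unstructured matrix is too rich for 24-30 people: 7 x 8 / 2 = 28 parameters for seven visits, and 15 for five.
- **Contrast:** the arm-by-visit contrast at week 24 (before the interruption) as the main comparison; other visits are supportive.
- **Values below the assay limit:** substitution at one stated fixed value in the main model, with a censored (Tobit-type) mixed model as sensitivity analysis. These are separate models, because REML with Kenward-Roger does not itself handle left-censoring.
- **Visits:** align the sampling times in sections 3.5 and 8.1, and say who contributes a week-48 sample.

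If the sponsor keeps the ANOVA, the minimum is to name the contrast, a Greenhouse-Geisser or Huynh-Feldt correction, and the missing-sample rule. The loss of incomplete participants would then remain.

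Cost: SAP wording and slightly more analysis work, with no new samples or participants. The mixed model relies on data being missing at random, which is least secure at week 48; this is one reason to make week 24 the main contrast.

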### 3. Plasma HIV-1 RNA:

Plasma HIV-1 RNA levels will be measured by a routine clinical assay (Cobas Taqman; detection limit 20 copies/mL), a transcription mediated amplification (TMA)-based assay (detection limit 12 copies/mL) and/or a single copy assay (detection limit 1-2 copies/mL). Fishers exact or chi-square test will be used to compare the proportion of subjects in both groups with detectable viremia during each romidepsin treatment.

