
Statistical Methodology
	
The Wilcoxon-Mann-Whitney will be used to determine changes from baseline to the pre-ATI time-point in reservoir size for each group. Fishers exact or chi-square test will be used to compare the proportion of subjects in both groups with detectable viremia during each romidepsin treatment. Functional properties of cytotoxic T cells and NK cells will be correlated to changes in total HIV-1 DNA and IUPM. Flow cytometry data will be evaluated by Boolean partitioning of NK and T cell responses into distinct responding populations (Lamoreaux et al., 2006).
 
Finally, correlation analysis will be performed to identify the markers most likely associated with time to viral rebound. As exploratory analysis, a linear regression model will be used to determine predictors of log-transformed time to viral rebound in both arms. P values <math><0.05</math> will be considered statistically significant.

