#### Exploratory Objectives:

- Evaluate the effects of romidepsin plus 3BNC117 or romidepsin alone on HIV-1 transcriptional activity and plasma HIV-1 RNA in ART-treated HIV-1-infected individuals
- Evaluate the immunomodulatory effects of romidepsin plus 3BNC117 or romidepsin alone in ART-treated HIV-1-infected individuals.
- Evaluate the pharmacokinetics of romidepsin in HIV-1-infected individuals

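### The only planned between-arm test of plasma HIV-1 RNA uses detectable yes/no; a rank test on the single copy values should be added, with a gain that depends on the fraction detectable

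*Combined protocol and SAP*

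**What the plan says.** Section 3.5 lists plasma HIV-1 RNA as a secondary endpoint. Section 3.3 places the matching objective among the exploratory ones: "on HIV-1 transcriptional activity and plasma HIV-1 RNA in ART-treated HIV-1-infected individuals".

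Section 8.1, item 3, opens with "Plasma HIV-1 RNA levels will be measured by a routine clinical assay" and adds TMA and/or a single copy assay. Its one inferential sentence is "Fishers exact or chi-square test will be used to compare the proportion of subjects in both groups with detectable viremia during each romidepsin treatment". The Statistical Methodology part of the Study Schema repeats the instruction to "compare the proportion of subjects in both groups with detectable viremia during each romidepsin treatment". No other between-arm test of plasma RNA appears. Item 5 of section 8.1 provides descriptive summaries of continuous data.

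Section 6.2.12 describes the assays:
- Cobas has a numerical range starting at 20 copies/mL.
- For TMA, "TMA results are considered binary and defined as positive or negative according to assay outcomes".
- "Single copy assay has a detection limit of 1-2 copies HIV-1 RNA/mL of plasma". This assay is run at baseline (week -2 and day 0) and 1 day after the second romidepsin infusion of each cycle.

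The plan does not say which assay or limit defines a detectable result, or which of the two tests applies.

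**The concern.** Two of the three assays can return a level, and the planned comparison uses only whether the level passes the limit. A participant at 2 copies/mL and one at 60 copies/mL count the same on the single copy assay.

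This could matter because section 3.1.1 says low-level viremia persists on suppressive ART, and section 3.1.3 reports that romidepsin activated HIV RNA expression at the dose used here. One day after an infusion, with a limit of 1-2 copies/mL, most participants in both arms may be positive. The yes/no measure then has little room to separate the arms, and a real fall in level under 3BNC117 could go undetected by the only formal test. No reason for the cut is given. Elsewhere section 8.1 analyses time to rebound, IUPM and cell-associated nucleic acids on their measured scale.

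**Working it through.** **1. The plan's own figure.** The only full-sample power statement (section 8.2) concerns the primary endpoint: 12 per arm, SD 10 days, difference 13 days, 5% level, minimum-ARE method. Standardised difference 13/10 = 1.3; effective size 12 × 0.864 = 10.37 per arm; noncentrality 1.3 × √(10.37/2) = 2.96. A two-sided noncentral t gives 80.1%, against the stated 80%. It reproduces. For plasma RNA the plan states no effect, SD, detectable fraction or power.

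**2. Inputs.** From the documents: 15 per arm enrolled; 12 per arm after about 20% dropout (30 × 0.8 = 24); 5% level; Fisher or chi-square. Assumed, because the documents are silent: log10 RNA is normal with equal SD in both arms; arm A is lower by d = 0.8 to 1.2 SD; the detection limit is set so that a fraction p_B of arm B is detectable; tests are two-sided.

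**3. Formulas.** The detectable fraction in arm A is p_A = Φ(Φ⁻¹(p_B) − d). For p_B = 0.90 and d = 1.0, p_A = Φ(1.28 − 1.0) = 0.61. The tests are Fisher's exact, uncorrected chi-square, and Wilcoxon-Mann-Whitney with tie correction, all undetected values tied at the lowest rank.

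**4. Power at 15 per arm, d = 1.0** (6,000 simulated trials per row; exact enumeration of the two proportion tests agrees within about 2 points):

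| Detectable B / A | Fisher | Chi-square | Wilcoxon | Wilcoxon − chi-square |
|---|---|---|---|---|
| 50% / 16% | 33% | 54% | 54% | 0 |
| 80% / 44% | 38% | 55% | 68% | 13 |
| 90% / 61% | 30% | 47% | 70% | 23 |
| 95% / 74% | 19% | 34% | 72% | 38 |

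Over 12-15 per arm and d = 0.8-1.2, the gain over chi-square is about 19-38 points at 90-95% detectable and 6-14 points at 80%. At 20-50% it is about −3 to +3 points.

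**5. Why the gap to Fisher is wider.** With equal detectable rates of 10-50% and 12 per arm, Fisher's actual type I error is 0.2-2.3%. Chi-square reaches up to 6.4%. The Wilcoxon test stays at 4-5%. Fisher therefore loses power through its conservatism on the same yes/no data, apart from any loss due to the cut.

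**6. A different alternative.** Suppose 3BNC117 acts all-or-none: fewer arm A participants are detectable, and detected values are distributed as in arm B.

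| n per arm | Detectable B / A | Fisher | Chi-square | Wilcoxon | Wilcoxon − chi-square |
|---|---|---|---|---|---|
| 12 | 90% / 50% | 43% | 61% | 39% | −22 |
| 15 | 90% / 50% | 54% | 73% | 48% | −25 |
| 15 | 95% / 55% | 64% | 80% | 49% | −31 |

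The order reverses: the rank test is behind chi-square by about 20-30 points, and here behind Fisher as well.

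**The case against.** The strongest case for the plan has four parts.

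- **The size is not a property of the trial.** A reader might infer from the gap to Fisher (13 to 54 points when 40-95% of arm B is detectable) that the cut itself costs that much. The documents do not support this. They allow chi-square as well, part of the gap is Fisher's conservatism, and they give no viremia distribution. On a wider assumed grid (0.5-1.3 SD, 10-90% detectable, either direction) the gain over chi-square with censoring runs from −3 to 86 points and is below 13 points in 75% of scenarios. This part stands.
- **Replacement would not be a clear improvement.** A reader might conclude that the rank test should displace the proportion test. The protocol's stated mechanism includes clearance of virus and infected cells, so an all-or-none effect is plausible, and the proportion test is then the better one. It is also the only comparison that applies to all three assays. This part stands.
- **Coverage is limited.** The single copy assay is run after only the second infusion of each cycle. Participants enter suppressed below 50 copies/mL, so many Cobas values may lie under 20 copies/mL, where ranking adds little. This part stands, and it points to the single copy assay as the place for the added test.
- **Levels will be reported anyway.** Section 8.1 requires descriptive summaries of continuous data, and section 3.3 treats plasma RNA as exploratory. This lowers the stakes. It does not supply a formal comparison of levels for an endpoint that section 3.5 calls secondary.

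**Conclusion.** The point holds in a limited form. Detectable yes/no by Fisher or chi-square is the only planned between-arm test of plasma HIV-1 RNA, and it discards levels that the single copy assay and, above 20 copies/mL, the Cobas assay already provide. The undefined term for detectability and the open choice of test add to the problem.

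The step 4 gains rest on the assumed log-normal shift and equal SDs. They are material only if most of arm B is detectable, which is plausible for the single copy assay but not established. Under an all-or-none effect the sign changes. No single figure for lost power can be quoted, and the primary conclusion of the trial is unaffected. An added rank test is justified; dropping the proportion test is not.

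**What to change.** In section 8.1, item 3, and in the synopsis:

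1. Keep the comparison of proportions detectable. Name one test, and state the assay and limit that define a detectable result.
2. Add: *For the single copy assay, HIV-1 RNA copies/mL 1 day after the second romidepsin infusion of each cycle will also be compared between arms with the Wilcoxon-Mann-Whitney test, undetected results assigned the lowest tied rank.*

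This is a wording change. It uses samples and assays already planned and needs no more participants. The cost is one additional secondary test per cycle, with a gain that depends on the fraction detectable and may be nil.
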